	While playing the game I had a vivid image of my character.
	At points, I had a hard time making sense of what was going on in the game.
	My understanding of the characters is unclear.
Narrative Engagement Scale	I had a hard time recognizing the thread of the story.
	I found my mind wandering while using the game.
	While using the game I found myself thinking about other things.
	I had a hard time keeping my mind on the game.
	While using the game, my body was in the room, but my mind was inside the world created by the story.
	The game created a new world, and then that world suddenly disappeared when the game ended.
	At times during the game, the story world was closer to me than the real world.
	The story affected me emotionally.
	During the game, when a main character succeeded, I felt happy, and when they suffered in some way, I felt sad
	I felt sorry for some of the characters in the game.

Below is the presence Self Assessment Manikin, with the instructions provided to participants:

Please use the figures below to indicate your feelings or emotional response to the game. The pictures go from a person who feels he or she is INSIDE THE PICTURE, A PART OF THE STORY, A PART OF THE ACTION on the left end, to a person who feels he or she is OUTSIDE THE PICTURE, REMOVED OR SEPARATED FROM THE STORY, NOT PART OF THE ACTION on the right end. Please circle the number for the picture, or the space between any two pictures, that best represents how you felt while using the app.

Counseling content example

Below, we present an example from our weekly brief counseling guides. The content and structure of the guides was taken from previous studies performed by co-mentor [name]. The themes for each week reflect standard behavior change counseling content and techniques, such as stimulus control, problem-solving, goal-setting, etc.

Week 3. Uncovering Barriers

[Discuss exercise progress report abstracted from application – ask for totals from the feedback screen(s)]

Last session we discussed finding times to fit in exercise. You mentioned that you wanted to try fitting in exercise _____ . Did you try it? Did you develop plans for the rest of the week? (YES NO) Were you able to fit in exercise in times that you hadn't before? What were they? _____

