meeting; an assessment at 6 months, and a final assessment at 12 months. Participants may attend an additional visit for randomization if we do not have a valid physical activity measurement. A battery of physiological and anthropometric measures will be performed at all assessments, and psychosocial outcomes will be measured by questionnaire. Questionnaires will also be completed by mail at 3 and 9 months. The study is designed such that regular intervention contacts will occur for the first 6 months. The period between 6 and 12 months will be monitored as a maintenance period, to determine whether behaviors are maintained in the absence of further counseling. Participants will receive \$25 gift cards at the 6 month and 12 month assessments for a total of \$50 incentive. They will also keep the mobile device as an additional incentive. The flow of the trial is displayed in **Table 6.3**. This pattern will be repeated for each cohort.

Personnel conducting the study will include a clinical research coordinator and two graduate research assistants. The research coordinator and one of the graduate research assistants will perform counseling calls, oversee monitor data, and provide technical assistance, while the other research assistant (blinded to participant group assignments) will conduct assessments. During the maintenance phase of this intervention (6 – 12 months), the research coordinator will continue to make monthly phone and mail contact to encourage continued participation (e.g., thank you and reminder postcards, calls to check for changes in contact information). No counseling content will be offered during these contacts.

Table 6.3. Timeline of trial assessments and phone contact by month

Month	0	1	2	3	4	5	6	7	8	9	10	11	12	
Assessments	Base-line			By mail			6 month			By mail			Final	
Calls		Weekly calls			Monthly calls			No counseling calls; maintenance period						
Study materials		Participants use mobile apps daily												

F.3. Participants and procedure (Aims 2 – 4)

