6. We will ask the participants several questions about their feelings about the study during a brief interview. The questions will be similar to those in the questionnaires, but the interview will allow the participant to provide more detailed answers. Topics will include how they felt about the mobile device, aspects of the game or monitor that were motivating to the participant. The interview will be audio recorded.

We will give the option to participants to complete an assessment visit when the recommended guidelines are lifted, and we are able to have a face to face visit. The visit may be completed only if participant is within a two-month period from their scheduled appointment.

Session 4. 12-month assessment (approximately 1 hour)

The visit will be conducted using teleconference communication (examples: via phone, skype, zoom)

Ongoing participants will complete Session 4: 12-month assessment using teleconference. Some of the assessment will need some modification due to our current situation and to ensure the safety of our subjects, staff and community. The following assessment will be conducted via teleconference:

1. Height and weight- we will obtain self-reported height and weight. If possible, we will obtain measurements at a future face to face visit if available.
2. Physical fitness- we will not collect this information during our scheduled visit. If possible, we will conduct this at a future face to face visit if available.
3. Physical function- we will not collect this information during our scheduled visit. If possible, we will conduct this at a future face to face visit if available.
4. We will ask the participants questions about their physical activity, their motivation for exercise, and their physical and emotional quality of life using teleconference call. Study staff will document the answers.

5. We will mail you an activity monitor. For the participant to wear for 7 days, for at least 10 hours per day. We will also mail a time log for participants to document the time they wear the activity monitor. We will provide mailing supplies to use to mail back the activity monitor.

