At the 6 month assessment or 12 month assessment (if not collected at 6 months), participants will discuss intervention acceptability and individualization during in-depth interviews, which have been recommended as a method for improving the cultural sensitivity of interventions.¹⁵⁷ The interview guide will include questions related to how well the app met their individual needs and if they felt it could be tailored to their preferences. We will concentrate on personal barriers to physical activity and how apps could be individualized to better address those barriers. The questions about narrative, for the enhanced group only, will qualitatively investigate potential effects of narrative transportation on attitudes, motivation, and behavior. In addition to interviews with participants, we will also recruit 10 stakeholders from the community and ask them the same questions after a brief orientation to the study materials to be discussed. Stakeholders will be identified via pre-existing stakeholder networks and previous participants who have expressed interest in helping with intervention adaptation. Results of these interviews will be used to further adapt the intervention for better cultural sensitivity. **Table 6.7** shows example questions.

Table 6.7. Selected questions from interview guide

Topic	Question
Individualization	Did you feel that the app was something you could easily adapt to fit your needs and preferences? Is there a way the app could have been better designed to be more appropriate for you or someone like you?
Narrative	How much did you feel like the characters in the game resembled you? Did playing as the main character make you feel differently about yourself?

F.7. Power and sample size

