The primary endpoint of this study will be behavioral change in physical activity at 6 months (Aim 1). Our primary hypothesis is: Participants who receive the enhanced intervention will spend more minutes per week in moderate-vigorous physical activity at 6 months than will those in the standard group. To test this hypothesis, we will use an analysis of covariance to test the difference between groups at 6 months, controlling for baseline. Missing data will be imputed. As a secondary analysis, we will use linear mixed modeling to investigate changes in physical activity over time at baseline, 6, and 12 months. This procedure will provide necessary information for powering a subsequent larger trial that will require complex modeling of multiple time points. We will also use multiple imputation techniques prior to all analyses to ensure that missing data due to attrition do not bias our results. Analyses will be performed using SAS 9.2 (SAS, Inc., Cary, NC). [name] and the research assistants will conduct all analyses in collaboration with biostatisticians from the biostatistics key resource in the Institute for Translational Sciences. Outcomes and effect sizes for other variables will be assessed using the same protocol.

Interviews with participants and stakeholders will be transcribed and coded by two trained coders. Code lists will initially be derived from Self-Determination Theory and theories of narrative transportation. Then, coders will use grounded theory to derive codes based on themes brought up by participants.¹⁶³ We have successfully used this procedure in the past.⁹² NVivo qualitative software will be used to code and compare codes across

multiple coders.

F.10. Potential limitations and alternative approaches

Several limitations might hinder the project's progress.

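### The plan does not keep the blinded assessor away from an arm-revealing interview at the 6-month assessment, so blinding of the in-person 12-month walk and function tests is not protected

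*Combined protocol and SAP*

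**What the plan says.** **Staffing (F.1).** "Personnel conducting the study will include a clinical research coordinator and two graduate research assistants". The coordinator and one assistant make the counselling calls, oversee monitor data and give technical help, "while the other research assistant (blinded to participant group assignments) will conduct assessments". No other assessor is named for any visit. E.4 says that a mentor will help with the activity, function and fitness measures, without stating whether she is blinded.

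**Interview timing.** F.6 (Acceptability and process measures) sets it "At the 6 month assessment or 12 month assessment (if not collected at 6 months"), and Aim 4 says the same for all 120 participants. The COVID-19 text in F.4 lists it as item 6 of Session 3, the six-month assessment: "We will ask the participants several questions about their feelings about the study during a brief interview".

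**Interview content.** The COVID-19 text includes "aspects of the game or monitor that were motivating to the participant" among the topics. F.6 adds: "The questions about narrative, for the enhanced group only, will qualitatively investigate potential effects of narrative transportation".

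**Tests at stake (Table 6.5).** The six-minute walk and four Senior Fitness Test items (chair stand, back scratch, chair sit and reach, 8-foot up and go) are done at 0, 6 and 12 months. Aim 1 names function and fitness at 6 and 12 months.

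**Primary endpoint (F.6, F.8).** Accelerometer minutes per week of moderate-vigorous activity at 6 months.

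**The concern.** The plan promises a blinded assessor, and that promise matters most for the walk and function tests. These are counted, timed or measured, but they depend on the participant's effort and on how the tester encourages and instructs. The only person named to conduct assessments is the blinded assistant, and the interview is one element of an assessment. An interviewer who asks about a zombie story or a walking log knows the arm from then on. If the same person runs the tests six months later, the 12-month comparison of fitness and function is made by an assessor who knows the allocation. Any resulting bias would most plausibly favour the arm the trial hopes will win. Month 12 is also where the trial looks for maintenance, which section D calls the main focus of the intervention.

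**Working it through.** The plan has no figure to reproduce on this point. The check is a cross-reading, followed by an illustration of scale.

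**Step 1. Who assesses?** F.1: one blinded assistant. The other two staff counsel participants and so know the arm.

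**Step 2. Is the interview part of an assessment?** Yes by timing in Aim 4 and F.6, and as a numbered item of the six-month assessment in the COVID-19 text.

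**Step 3. Does it disclose the arm?** Yes. Its topics differ between game and monitor, and one block of questions goes to one arm only.

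**Step 4. Is the interviewer named as someone else?** No. The COVID-19 text says only that the study team will ask. F.6 names nobody.

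**Step 5. Is there an order within the visit?** No. Session 3 lists the interview after fitness and function, but the list is not presented as a sequence, and those tests are not done at that remote visit.

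**Step 6. Is there a separate assessor at month 12?** None is given.

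**Step 7. Which measurements are exposed if the assessor interviews?**
- In-person 12-month tests in participants interviewed at 6 months: 4 Senior Fitness Test items + 1 walk = 5 tests.
- Tests at the same visit, at 6 or 12 months, if the interview precedes them.
- Not exposed: remote pandemic visits, where fitness and function are not collected. A later face-to-face visit, allowed within two months of the appointment, would be exposed.
- Not exposed: the accelerometer endpoint, which no assessor scores.

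**Step 8. Scale, under assumed shifts.** The documents give no observer-bias size, so 0.1, 0.2 and 0.3 SD are assumptions. With N = 120 and the 20% attrition allowed for in F.7, n = 120 × 0.8 / 2 = 48 per arm. For a two-sided 5% two-sample t-test with no true effect and a mean shift of d SD between arms, the noncentrality is d × √(n/2) = d × √24.

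| Assumed shift (SD) | Noncentrality (n = 48) | False-positive rate, 48 per arm | Same, 60 per arm |
|---|---|---|---|
| 0 | 0 | 5% | 5% |
| 0.1 | 0.49 | 7.7% | 8.4% |
| 0.2 | 0.98 | 16.3% | 19.2% |
| 0.3 | 1.47 | 30.7% | 37.1% |

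The shift is the average over everyone analysed. If a 0.2 SD shift reached only half of the participants, evenly across arms, the mean shift would be 0.2 × 0.5 = 0.1 SD and the rate about 7.7%. The table uses an unadjusted t-test, whereas F.8 plans baseline-adjusted analysis. It shows order of magnitude only.

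**The case against.** The strongest reply is that no sentence gives the interview to the blinded assistant. F.1 describes assessments as physical measures and questionnaires and does not mention the interview. Placing it at the 6-month assessment fixes when it happens, not who does it, and two unblinded staff are available. This stands in part. A reader might infer that the 12-month tests are in fact unblinded, or that the assessor knows the arm by then. The documents do not support that, because the interviewer is never identified. They also contain nothing that separates the two roles, and the literal wording of F.1 points to the assessor.

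A reader might also infer leaks by other routes. These are speculative:
- **Transportation scale.** Only the game arm completes it, but F.6 allows self-report measures on paper or a secure website, so no assessor need see it. During the pandemic, unspecified study staff record questionnaire answers.
- **Analysis.** F.8 says that the principal investigator "and the research assistants will conduct all analyses" without excepting the blinded assistant. It gives no timing, and F.10.a and F.11 reserve the last year mainly for analysis and data cleaning. The 6-month paper in Year 4 is only an example in a table of potential manuscripts.

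Three further points are fair. The outcomes are secondary in a trial that B.5 places before full efficacy testing. Participants know their arm and may reveal it whoever interviews them. Enrolment is closed according to the COVID-19 text, so a change reaches only the visits that remain. These limit the consequence and the reach of a fix, but they do not supply the missing safeguard.

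**Conclusion.** The point holds as an unprotected risk, not as a demonstrated loss of blinding. On the plain reading of F.1 with Aim 4, F.6 and the COVID-19 text, assessor blinding is not secured for the in-person 12-month six-minute walk and Senior Fitness Test in participants interviewed at 6 months. The same applies to same-visit tests if the interview comes first. How many participants are affected cannot be derived: it depends on who interviewed, when, and whether the 12-month visit was in person. The bias cannot be sized either. The 7.7% to 30.7% range rests entirely on assumed shifts of 0.1 to 0.3 SD averaged over 48 per arm and is not evidence about this trial. The primary analysis does not change. The correction is cheap and worth making, because without it the fitness and function results cannot safely be reported as blinded.

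**What to change.** State in F.1 and F.6 that:
- the coordinator or the counselling research assistant, both already unblinded, conducts the interview and any arm-specific scale that staff administer;
- this happens after all performance tests at that visit;
- the blinded assistant does not handle interview recordings, transcripts or arm-labelled data until the last 12-month test is done.

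For visits already completed, report who conducted the interviews and whether the 12-month assessor knew the arm.

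The cost is a few sentences and a reassignment among existing staff, with no hires. The downside is that participants may answer slightly more positively to someone who counselled them, which could inflate the Aim 4 acceptability findings. The change lowers the risk of unblinding but cannot stop participants from disclosing their arm themselves.

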A pre-experimental pilot study (N = 10, 4 ethnic/racial minority) using mobile devices in older adults included two women who were long-term BC survivors. The study protocol, which involved provision of a tablet and activity monitor, was found to be feasible and acceptable over the brief intervention period (6 weeks). Participants wore the monitors as instructed and synced their data daily or multiple times per day. Adherence was very good, with monitors worn and synced 402 out of a possible 420 days. Participants significantly improved their fitness and function compared to baseline. Measures of acceptability showed that participants found the tablet, monitor, and application to be useful and enjoyable.

An additional pre-experimental pilot (N = 10, 3 ethnic/racial minority) is investigating one of the games to be used in the proposed study (*Zombies, Run!*). We provided smartphones with the game app to adult women (18 – 69), six of whom were over 55. The study is not yet complete, so we cannot estimate adherence. However, qualitative acceptability measures taken at the midpoint indicate two major reported reasons for non-adherence: preference for using the participant’s own phone and preference for measuring lifestyle activity rather than (or in addition to) planned activity. All participants had no problems using the smartphones provided and reported finding the game and story very motivating. Despite these positive feelings, the requirements surrounding use of the game were felt to be onerous. Unlike in the above trial, participants were required to remember to turn on the app prior to planned walking bouts. Several women mentioned forgetting to carry a second phone (since they already had their own cell phone), or felt that the requirements to remember a second phone and to remember to turn on the app were burdensome. We hypothesize that using a non-smartphone mobile device (like an iPod or iPad), allowing use of participants’ own phones, and providing a choice of apps that include lifestyle monitoring (i.e., that doesn’t require pre-planned activity bouts) would improve adherence.

E.3. Behavior change techniques and game mechanics

Table 6.2. Differences between game and monitor apps

	Games		Monitor
	Zombies Run!	The Walk	App
Behavior change techniques			
Goal-setting		x	x
Self-monitoring	x	x	x
Feedback	x	x	x
Game mechanics			
Competition/conflict	x		
Freedom of choice	x	x	
Dynamic/ephemeral goals		x	
Narrative	x	x	
Novelty/surprises	x	x	

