Pick-ups	x		
Resource management	x		
Rewards	x	x	
Social status/reputation/support	x		
Time limits/pressure	x	x	

[name] and colleagues recently compared the content of active video games and activity monitors to standard taxonomies of behavior change techniques.⁶⁶ These analyses were used to choose games and activity monitors suitable for this study. **Table 6.2** compares two narrative-based active game apps to an electronic activity monitor app. Both the game apps and the monitor app include techniques that, when implemented, are associated with increased physical activity.^{94,95} Thus, standard intervention components are equivalent across the two app types. The major differences lie in game mechanics, which are common in the two games and entirely absent from the monitor app. Thus, a comparison of the games to the monitor would isolate the effects of game mechanics while providing both groups with the standard social-cognitive intervention components necessary in a behavioral physical activity intervention.

E.4. Mentor areas of expertise and previous studies

The three co-mentors were chosen to address specific areas in which [name] requires more training and education. [name] is an expert in aging, health disparities, and comparative effectiveness research in cancer. His perspective as a practicing geriatrician and health services researcher will be extremely useful for refining intervention components to be feasible for dissemination. He has authored or co-authored many papers on topics related to this research program, including on aspects of race related to obesity,^{96,97} breast cancer treatment,^{98,99} physical activity as an indicator of health in older adults,¹⁰⁰⁻¹⁰² patient-oriented outcomes in older adults,^{103,104} interventions to improve outcomes in BC patients,¹⁰⁵⁻¹⁰⁷ and psychosocial aspects of cancer treatment and survivorship.^{106,108-111}

[name], at nearby M.D. Anderson Cancer Center, will provide expertise and mentoring specific to behavioral physical activity intervention in women cancer survivors. She is a leading expert in this field with significant expertise in intervention testing¹¹² and adaptation.¹¹³ Her primary area of expertise lies in the application of health behavior theory to understanding physical activity in this population.^{29,114-117} She has implemented multiple large-scale interventions among survivors, including breast cancer survivors.^{112,118,119}

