- 2)** Provision of one mobile game application
- 3)** Provision of online currency (e.g., iTunes gift cards) to purchase music to be used in the game (\$50)
- 4)** Brief counseling phone calls that occur weekly for 3 months, then monthly until 6 months

Participants will be able to use their own smartphone devices should they wish to; however, we will provide an iPod Touch mobile device to ensure that they have access to a device compatible with the chosen apps. (It will also serve as an incentive, as iPod Touches can hold much more music and data than most smartphones and take high-quality pictures.) The iPod Touch is similar to an iPhone, but does not require cellular service for use and is primarily an app and music use device. Thus, we believe that it should be perceived as a more acceptable mobile device than a smartphone, despite its very similar functionality. In our preliminary studies (see pages 6.5 - 6.6) we found that smartphone-based interventions are acceptable among older women, but that allowing use of their own phone and/or providing a non-phone mobile device is preferred.

The game to be used is *Zombies, Run!*, created by developers Six to Start. This game was chosen due to its unique blending of an involved narrative storyline with game mechanics and extensive interactive behavioral tools. *Zombies, Run!* is a game that encourages bouts of 30 – 60 minutes of walking, jogging, or running. The accelerometer of the mobile device measures steps taken and provides extensive feedback. **Table 6.2** on page 6 shows several of the game mechanics most commonly used in the game, and **Figure 6.2** shows screenshots of the game. Players use the mobile device to set up the game, but during exercise the device is held or worn on the arm (armbands and headphones are included with the mobile device). The game plays user-chosen music and places clips of an audio narrative in between those songs, to provide an illusion of other characters “radioing in” while the player travels by foot in a post-apocalyptic world. While songs are played, the game provides audio cues when players “pick up” virtual supplies or are chased by zombies. Zombie chases (which can be turned off) require players to increase their speed by 20% for one minute in order to out-run their pursuers. If the zombies catch the player, they “drop” some of their virtual supplies to distract the zombies and escape.

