This study is powered to detect differences between the two groups in minutes of moderate-vigorous physical activity at 6 months. We used G*Power to calculate sample size based on several studies that are similar to this one. Similar trials of telephone counseling and activity monitoring among BC survivors produced effect sizes ranging from 0.53 to 0.82.¹⁵⁸⁻¹⁶⁰ Because our study includes a low-intensity control group that we anticipate will produce a weak effect at 6 months, we have powered for a conservative effect size for physical activity at 6 months of approximately $d = 0.65$, which would require an N of 78 for 80% power at an alpha of 0.05. This effect size translates to a between groups difference of approximately 20 minutes per week ($SD = 30$ minutes). An N of 120 would allow a fully powered test of physical activity even in the case of 20% attrition and higher variability than expected (i.e., lower effect size).

Similar studies that investigated maintenance are so few (three to our knowledge) and show such disparate results that power was difficult to calculate for this effect. For example, Rogers et al. report large differences in change scores between groups from baseline to the end of maintenance (79 vs. -22 minutes per week; 3 month follow-up),¹⁶¹ whereas Vallance et al. report smaller differences (24 vs. -14 minutes per week; 6 month follow-up).¹⁶² Even assuming large standard deviations for these change scores, our sample should be sufficient to detect group differences during the maintenance period as well.

F.8. Statistical analysis

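### Does calling the standard arm low-intensity in F.7 contradict its matched design and undermine the planned d = 0.65?

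*Combined protocol and SAP*

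**What the plan says.** F.7 (Power and sample size) starts from published work: "Similar trials of telephone counseling and activity monitoring among BC survivors produced effect sizes ranging from 0.53 to 0.82". It then chooses about d = 0.65, which it calls conservative, and introduces the choice with "Because our study includes a low-intensity control group that we anticipate will produce a weak effect at 6 months". It equates this with about 20 minutes per week at SD 30, obtains N = 78 for 80% power at alpha 0.05, and adds: "An N of 120 would allow a fully powered test of physical activity even in the case of 20% attrition and higher variability than expected".

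The standard arm is described elsewhere.

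- E.3 says of the apps: "Both the game apps and the monitor app include techniques that, when implemented, are associated with increased physical activity". It states that "standard intervention components are equivalent across the two app types", and that comparing them "would isolate the effects of game mechanics while providing both groups with the standard social-cognitive intervention components".
- F.1 gives both arms one call timetable and content.
- F.5 adds counsellor time in the standard arm so that attention is balanced, and bases its counselling on Social Cognitive Theory.
- F.4 gives the enhanced arm that basic counselling plus narrative counselling tied to the game.

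F.8 tests the 6-month difference by ANCOVA adjusted for baseline.

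**The concern.** F.7 appears to rest on a premise that the design removes. The cited range of 0.53 to 0.82 comes from counselling-and-monitoring trials, and the standard arm here also receives counselling and monitoring. What the trial tests is the increment from the narrative game and its counselling over an active comparator, and F.7 cites no effect size for that. "Table 6.2. Differences between game and monitor apps" seems to sharpen the point: it credits the monitor app with all three behaviour change techniques but *Zombies, Run!* with two, lacking goal-setting, and F.4 lists "Provision of one mobile game application".

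If the real increment were well below 0.65, the trial would often miss it. F.11 calls the study fully powered without naming a difference, so a non-significant result might be read as showing that games add nothing.

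**Working it through.** **Inputs.** From F.7: d = 0.65; cited range 0.53 to 0.82; difference 20 min/week; SD 30; alpha 0.05; N = 120; attrition 20%, so 120 × 0.80 = 96 observed. F.3 gives 1:1 allocation, so 48 per arm. F.7 does not state sidedness; 78 reproduces only as two-sided.

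**1. Reproduce F.7.** For a two-sample t-test with n per arm, the noncentrality is d × √(n/2) on 2n − 2 degrees of freedom.

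- n = 38: power 79.9%, just short.
- n = 39: 0.65 × √19.5 = 2.87, power 80.9%. Total 78, as stated.

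**2. Check the allowance for attrition and variability.** With n = 48, √24 = 4.899.

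| d | Noncentrality | Power |
|---|---|---|
| 0.65 | 3.18 | 88% |
| 0.58 | 2.84 | 80% |
| 0.53 | 2.60 | 73% |

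The 80% point is d = 0.578, or 0.578 × 30 = 17.3 min/week. For a 20-minute difference, the SD could rise from 30 to 20/0.578 = 34.6 before power fell below 80%. F.7's sentence is therefore true, with a modest margin. If all 120 were observed, power at 0.53 would be 82%.

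**3. The planned test.** ANCOVA scales the effective d by 1/√(1 − r²), where r is the baseline correlation. The documents give no r. Assuming r = 0.3 or 0.5, the 80% point falls to 0.551 (16.5 min/week) or 0.500 (15.0 min/week). To reach 80% power at d = 0.53 needs √(1 − r²) = 0.53/0.578 = 0.917, so r is about 0.40.

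**4. How large an increment is being asked for?** If the standard arm achieved everything the cited interventions achieved, the add-on alone would have to equal 0.65/0.82 = 79% to 0.65/0.53 = 123% of a cited effect. That comparison needs three assumptions the documents do not support: a standard arm equal to the cited interventions, additive effects, and a common SD and outcome scale.

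- The reference list titles one of the three cited trials as print materials and pedometers, which is not an app with calls.
- The maintenance reports quoted in F.7 show group differences of 79 − (−22) = 101 and 24 − (−14) = 38 min/week, which suggests a different scale from 20 with SD 30.

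**5. Is low-intensity incompatible with matched?** E.3, F.1 and F.5 compare the arms with each other. Other sections describe light contact in both: calls weekly for three months and then monthly (F.4), under 15 minutes (COVID-19 text in F.4), closed promptly beyond 20 minutes (F.10.d), with exercise unsupervised. Section B reports that adherence in skills-based programmes falls quickly, with 53% meeting goals by week 9 of 12. A weak control effect at month 6 is thus arguable from the document itself.

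**6. Table 6.2.** The technique count carries little weight. F.1 gives every participant a goal-setting visit, and *The Walk*, which the table credits with goal-setting, is pre-loaded as a backup (F.4).

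**The case for a change.** The strongest case for acting is that F.7's reason does not support its number. Light contact and fading adherence would affect the enhanced arm too, so they explain a weak control effect without explaining a large difference. Nor is 0.65 clearly conservative: the midpoint of the cited range is (0.53 + 0.82)/2 = 0.675. If the increment were half the planning value (d = 0.325, about 10 min/week; an assumption), power with 96 observed would be 35%, or 44% with r = 0.5. The unadjusted 95% interval has half-width 1.986 × 30 × √(2/48) = 12.2 min/week, so a null result would exclude 20 min/week only if the estimate were below 20 − 12.2 = 7.8.

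The criticism of the rationale stands: it is thin, and F.7 offers no estimate for the contrast tested. The low-power figures depend on an increment chosen for illustration. The feared misreading is not in the plan, which nowhere says that a null result will be taken as no effect. B.5 places the study between pilot and efficacy testing, with effect sizes among its intended products, so a missing prior estimate of the increment is partly why the trial is run.

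**Conclusion.** No change is needed. There is tension between F.7's description of the control and the matched design, but no strict contradiction, and no stated figure is wrong. The plan delivers the power it claims at its stated d: 80.9% with 78, and 88% with 96 of 120 observed. Its unadjusted margin runs to d = 0.58 (about 17 min/week at SD 30), with 73% power at 0.53; ANCOVA extends it by an amount set by an unstated baseline correlation.

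Whether 0.65 is realistic for the narrative game plus narrative counselling is a matter of judgement that the documents cannot settle. Revising the argument would gain nothing now: the COVID-19 text in F.4 says enrolment is complete, and the endpoint, test and sample size would stay as they are. The ANCOVA gives an adjusted difference with a standard error, and an analyst would normally report its confidence interval and read a wide null as inconclusive. These figures assume two-sided testing at 0.05, equal arms, 96 observed outcomes and SD 30.
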